9.1.2 Populations for Analyses

- All enrolled subjects: All subjects who signed an informed consent form and were registered.
- All randomized subjects: All subjects who were randomized to any treatment arm in the study.
- All treated subjects: All subjects who received any study drug nivolumab, ipilimumab or SBRT.
- Biomarker subjects: All randomized subjects with available biomarker data (PD-L1 expression status, Merkel cell polyomavirus expression, and other assays).

9.2 Endpoints

9.2.1 Primary Endpoint(s)

The primary endpoint is ORR. The primary endpoint of ORR will be the sum of the rate of complete response, partial response and stable disease of non-irradiated target lesions.

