Study Assessments: Objective response rate is the primary endpoint of the trial. The ORR will be calculated as the percentage of patients who had a complete or partial response that was confirmed by a subsequent radiologic imaging study or clinical exam according to irRECIST criteria among all the patients who received at least one dose of nivolumab and ipilimumab with or without SBRT.

- Screening.
- Treatment Period: Every 12 weeks (\pm 7 days) from first dose of study drug through 45 weeks (relative to the first dose of study drug)
- Follow-up Period:
 - a) Every 12 weeks (\pm 14 days) through 12 months for subjects who discontinued early from treatment (relative to the first dose of study drug)

- b) Every 12 weeks (± 21 days) if > 12 months through 24 months (relative to the first dose of study drug)
- c) Every 6 months (± 28 days) if > 24 months through and up to Year 5 (relative to the first dose of study drug).

Statistical Considerations:

Sample Size: From historical data, we will consider 17% response rate as not warranting further study. We will use 40% response rate as a promising result to pursue further study. In other words, we are interested in at least 23% (40% vs. 17%) improvement in treatment efficacy for arms B versus A. For each arm, using a Simon Mini-Max two-stage design with 10% type I error rate and 10% type II error rate, 16 patients will be enrolled in the first stage of the trial. If 2 or fewer patients respond, the treatment will be stopped. If 3 or more patients show a response, 8 additional patients (a total of 24 patients per group) will be enrolled. If the total number responding is 6 or less, we will conclude that the treatment is not effective. If both arms fail at the first or second stage, the trial will stop. No winner will be claimed. The sample size will be 32 if both arms fail at the first stage and 40 if only one arm fails at the first stage. If only one arm pass the second stage, the arm will be the winner. If both arms pass the second stage, we will use the posterior probability, $\Pr(B>A)$, (probability of the response rate in arm B higher than in arm A) to select the winner. A non-informative prior of beta distribution, $\text{beta}(1,1)$ in both arms will be used to calculate the posterior probability. Arm B will be claimed as the winner if $\Pr(B>A) > \delta = 0.8$.

Endpoints:

Primary Endpoint: Objective response rate in all randomized subjects

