1.5.5 Summary of Clinical Activity

Nivolumab Monotherapy

Several immune checkpoint inhibitors targeting PD1 or PD-L1 are being tested currently. A recent interim report of phase I/II trial of metastatic treatment-naive MCC patients on pembrolizumab reported 14% complete response rate¹⁰. Therefore, we anticipate a significant therapeutic efficacy of

nivolumab in MCC, which is being evaluated in an on-going multi-institutional clinical trial on Nivolumab alone for virus-associated cancers including MCC conducted by BMS.

Otherwise, the clinical activity of nivolumab was demonstrated in multiple tumor types. In CA209003³⁸ the clinical activity of nivolumab was demonstrated in melanoma, RCC, and NSCLC. Clinical activity was noted across a range of doses (0.1 mg/kg, 0.3 mg/kg, 1 mg/kg, 3 mg/kg, 10 mg/kg). In CA209003, as of the clinical cut-off date of 03-Jul-2012, a total of 304 subjects with melanoma, RCC, and NSCLC have been evaluated for clinical activity. A response of either CR or PR, as determined by investigator assessed tumor evaluations based on modified RECIST 1.1, has been reported at all dose levels. No responses (CR or PR) have been reported in subjects with colorectal carcinoma or castrate-resistant prostate cancer.

Among 106 subjects with advanced melanoma who received nivolumab and were evaluable for response, the preliminary objective response rates were 6/17 (35%), 5/18 (28%), 11/34 (32%), 7/17 (41%), and 4/20 (20%) for melanoma subjects treated at 0.1, 0.3, 1, 3, and 10 mg/kg, respectively. Duration of response range from 3.6 to 11.2, 1.8 to 9.2, 1.9 to 24.9, 9.2 to 22.4, and 17.0 to 25.7 months in the melanoma subjects treated at 0.1, 0.3, 1, 3, and 10 mg/kg, respectively. Stable disease over 24 weeks occurred in an additional 1/18 (6%), 4/34 (12%), 1/17(6%) melanoma subjects at 0.3, 1, and 3 mg/kg, respectively. Finally, the PFS-24 week was 41%, 33%, 48%, 55%, and 30% in melanoma subjects treated at 0.1, 0.3, 1, 3, and 10 mg/kg, respectively.

SBRT Monotherapy

The local control rate of irradiated tumors following SBRT is excellent. For instance, five-year local control rate stage I non-small cell lung cancer patients treated with 54 Gy in 3 fractions is in excess of 80%⁹⁶. On a particular note, MCC metastases treated with SBRT to 8Gy in a single fraction achieved complete responses in 45% of tumors with durable local control in 77% of treated tumors with a median follow up of 277 days²⁴.

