7.4 Efficacy Assessments

Study evaluations will take place in accordance with the flow charts in Section 5. Baseline disease assessments should be performed within 28 days prior to the first dose utilizing CT or MRI. In addition to neck, chest, abdomen, pelvis, and brain, all known sites of disease should be assessed at baseline. Subjects will be evaluated for progression of target lesions or for development of new metastases beginning 12 weeks (+/- 7 days) relative to the first dose of study treatment, and will continue to have surveillance assessment every 12 weeks (+/- 7 days) for the first 12 months. From > 12 months to 24 months after randomization, efficacy assessments should be every 12

weeks (+/- 14 days). From > 24 months until Year 5 after first dose of study treatment, efficacy assessments should be performed every 6 months (+/- 4 weeks).

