9 STATISTICAL CONSIDERATIONS

9.1 Statistical Design

The result of Nivolumab alone clinical trial for virus-associated cancers including MCC is pending, but the estimated objective response rate with Nivolumab alone is estimated around 17% based on Avelumab and Pembrolizumab trial for patients without prior immunotherapy exposure or previously failed prior immunotherapy (refractory). Therefore, we will consider a 17% response rate as not warranting further study. We will use a 40% response rate as a promising result to pursue further study. In other words, we are interested in at least 23% improvement in treatment efficacy for either one of the two arms: Nivolumab + SBRT + Ipilimumab (Arm B) or Nivolumab + Ipilimumab (Arm A). Since both treatments are experimental therapy in this targeted population, Simon two-stage design is used to evaluate the treatment efficacy. To determine the best treatment arm, we utilize a Bayesian posterior probability with Simon two-stage design in a two-arm randomized trial in order to have objective comparison between the two arms¹¹⁰. This design has several unique features: (1) Randomization reduces selection bias and allows a greater degree of comparability, (2) The Simon two-stage design will allow for termination of an ineffective drug earlier when compared to historical control data, and (3) The Bayesian posterior probability provides additional power to detect a definitive differential treatment effect. This design has been employed in various lung cancer trials at Moffitt Cancer Center.

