9.1.1 Sample Size Calculation

From historical data, we will consider 17% response rate as not warranting further study. We will use 40% response rate as a promising result to pursue further study. In other words, we are interested in at least 23% (40% vs. 17%) improvement in treatment efficacy for arms B versus A. For each arm, using a Simon Mini-Max two-stage design with 10% type I error rate and 10% type II error rate, 16 patients will be enrolled in the first stage of the trial. If 2 or fewer patients respond, the treatment will be stopped. If 3 or more patients show a response, 8 additional patients (a total of 24 patients per group) will be enrolled. If the total number responding is 6 or less, we will conclude that the treatment is not effective. If both arms fail at the first or second stage, the trial will stop. No winner will be claimed. The sample size will be 32 if both arms fail at the first stage and 40 if only one arm fails at the first stage. If only one arm pass the second stage, the arm will be the winner. If both arms pass the second stage, we will use the posterior probability, $Pr(B > A)$, (probability of the response rate in arm B higher than in arm A) to select the winner. A non-informative prior of beta distribution, beta(1,1) in both arms will be used to calculate the posterior probability. Arm B will be claimed as the winner if $Pr(B > A) > \delta = 0.8$.

Operating Characteristics

The operating characteristics of the design is evaluated by simulation (10000 times) using R software (www.r-project.org) with "clinfun" package. In particular, we are interested in the probability of (correctly) selecting an arm as superior to the other arm if it is truly superior, and conversely, the probability of (incorrectly) selecting an arm that is no better than the other arm.

Power Analysis

Power: Assuming that the true probabilities of response in arms B and A are 40% and 17%, respectively (scenario 1: 23% difference of response rate), the overall probability (power) of correctly choosing arm B as superior is 85% on the basis of superiority shown at the end of the trial.

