The probability of stopping arm A early and declaring arm B superior at the end of the trial is 81%. There are 9% of both arms passing the second stage with 4% claiming arm B as the winner by the Bayesian posterior probability. In a 18% difference of response rate, the overall power is 74% and 77% for the comparison of arms B and A with 35% versus 17% (scenario 2) and 40% versus 22% (scenario 3), respectively. Proportion of both arms passing the 2nd stage is 8% in scenario 2 (scenario 3: 23%), with 2% (scenario 3: 10%) claiming arm B as the winner by the Bayesian posterior probability.

Type I error

Type I error: In the null hypothesis of a 17% response rate in both arms, there are 9% misclassifying arm B as winner (i.e., 9% type I error). Among them, only 1% has both arms passing the 2nd stage, and less than 0.01% misclassify arm B as winner.

Summary

Summary: With $\delta=0.8$, the design has a 85% power to detect a 23% difference of response rate. The power decreases to a range of 74-77% to differentiate a 18% difference of response rate. The type I error is controlled at 9% when both arms have a 17% response rate.

Tables of Power Analysis

Scenario 1: Arm B=0.4 versus Arm A=0.17 (Overall power of Arm B= 85%)

	B.fail.stage1	B.fail.stage2	B.pass
A.fail.stage1	0.01	0.04	0.42
A.fail.stage2	0.01	0.03	0.39
A.pass	0	0.01	0.09

Both arms passing the 2nd stage: 9%. Among them, Arm B claims 4.31% as winner

Overall power of Arm B= 85%

Scenario 2: Arm B=0.35 versus Arm A=0.17 (Overall power of Arm B= 74%)

	B.fail.stage1	B.fail.stage2	B.pass
A.fail.stage1	0.02	0.08	0.38
A.fail.stage2	0.02	0.07	0.33
A.pass	0	0.02	0.08

Both arms passing the 2nd stage: 8%. Among them, Arm B claims 2.33% as winner

Overall power of Arm B= 74%

Scenario 3: Arm B=0.4 versus Arm A=0.22 (Overall power of Arm B= 77%)

	B.fail.stage1	B.fail.stage2	B.pass
A.fail.stage1	0.01	0.03	0.25

A.fail.stage2	0.01	0.03	0.41
A.pass	0.01	0.02	0.23

Both arms passing the 2nd stage: 23%. Among them, Arm B claims 9.89% as winner

Overall power of Arm B= 77%

Scenario 4: Arm B=0.17 versus Arm A=0.17 (Type I error= 8.89%)

	B.fail.stage1	B.fail.stage2	B.pass
A.fail.stage1	0.22	0.2	0.04
A.fail.stage2	0.2	0.19	0.04
A.pass	0.05	0.04	0.01

Both arms passing the 2nd stage: 1%. Among them, Arm B claims 0.01% as winner

Type I error= 8.89%

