9.3.2 Efficacy Analyses

9.3.2.1 Primary Endpoint Methods

Objective-response rate (ORR) including Complete Response (CR) rate, Partial Response (PR) rate, and Stable Disease (SD) rate will be calculated through exact binomial distribution with a 2-sided 95% confidence interval among patients who obtain a least one dose of study drug.

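### Section 9.2.1 counts stable disease in the primary ORR, while the synopsis counts only confirmed CR or PR and the 17%/40% design rates are objective response rates

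*Combined protocol and SAP*

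**What the plan says.** The primary endpoint is defined in more than one way.

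- **Section 9.2.1** (Primary Endpoint): "The primary endpoint of ORR will be the sum of the rate of complete response, partial response and stable disease of non-irradiated target lesions".
- **Section 9.3.2.1**, on the analysis of ORR: "Objective-response rate (ORR) including Complete Response (CR) rate, Partial Response (PR) rate, and Stable Disease (SD) rate will be calculated through exact binomial distribution". Read alone, this could be a list of rates to report.
- **Synopsis, Study Assessments**: "The ORR will be calculated as the percentage of patients who had a complete or partial response that was confirmed", with irRECIST as the criterion and no mention of SD.
- **Section 1.4.3**, the rationale for the endpoint, names overall, complete and partial response and leaves SD out.

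The design rates are objective response rates. Section 9.1 says "the estimated objective response rate with Nivolumab alone is estimated around 17% based on Avelumab and Pembrolizumab trial", and 40% is the rate worth pursuing. The stage 1 rule in 9.1.1 reads "If 2 or fewer patients respond, the treatment will be stopped", without defining a response. The summary in 9.1.1 claims: "The type I error is controlled at 9% when both arms have a 17% response rate".

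The ORR denominator also varies. The calculation sentence in the synopsis and Section 9.3.2.1 use patients with at least one dose. The synopsis Endpoints line and its Analyses paragraph use all randomized subjects.

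**The concern.** The stage 1 stop, the final cut-off and every operating characteristic in 9.1.1 are calibrated to a null of 17% CR+PR. If the 9.2.1 definition is carried into that rule, an arm whose CR+PR rate is 17% is judged at 17% plus its SD rate. The futility stop then weakens, and an arm no better than the historical control passes more often than planned.

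Two analysts could also reach opposite conclusions from the same data. Take an arm that has passed stage 1 and ends with 4 responders and 3 patients with SD among 24. Under the synopsis it has 4 successes and fails, since 6 or fewer is a failure. Under 9.2.1 it has 4 + 3 = 7 and passes.

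**Working it through.** **Inputs.** From 9.1.1: n1 = 16, stop at 2 or fewer; n = 24, fail at 6 or fewer; beta(1,1) priors and a threshold of 0.8 for naming arm B. From 9.1 and 9.1.1: null 17%, target 40%. From 1.5.5, the only SD rates in the document: "Stable disease over 24 weeks occurred in an additional 1/18 (6%), 4/34 (12%), 1/17(6%) melanoma subjects".

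**Formulas.** With p the per-patient success probability:

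- P(stop at stage 1) = P(Bin(16, p) ≤ 2)
- P(pass) = Σ over x = 3 to 16 of P(Bin(16, p) = x) × P(Bin(8, p) ≥ 7 − x)
- P(at least one arm passes) = 1 − (1 − P(pass))², with both arms at the same p
- P(B named winner) = P(pass) × (1 − P(pass)) + P(both pass and Pr(B>A) > 0.8)

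**Step 1: reproduce the plan.** A minimax search at 17% versus 40% with 10%/10% errors returns 16/2 and 24/6. Exact per-arm error is 9.78% and power 90.13%. With both arms at 17%, B is named winner with probability 0.0882 + 0.0003 = 0.0885, against 8.89% in 9.1.1. With B at 40% and A at 17% it is 85.5%, against 85%. The stated figures are therefore correct when p is the rate to which the 17% refers.

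**Step 2: add SD.** Keep true CR+PR at 17% in both arms and set p = 0.17 + SD.

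| SD | p | Stop at stage 1 | Arm passes | B named winner | At least one arm passes |
|---|---|---|---|---|---|
| 0% | 0.17 | 47% | 9.8% | 8.9% | 19% |
| 5% | 0.22 | 28% | 26% | 20% | 45% |
| 6% | 0.23 | 25% | 30% | 22% | 51% |
| 10% | 0.27 | 15% | 48% | 27% | 73% |
| 12% | 0.29 | 11% | 57% | 28% | 81% |
| 20% | 0.37 | 3% | 84% | 26% | 97% |

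The probability that an arm passes reaches 50% at p = 0.275, that is, at SD of about 10.5 points. The winner probability levels off because at high p both arms usually pass, and the 0.8 threshold then seldom favours B. The loss of control shows in the per-arm and any-arm columns.

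**Step 3: unrounded fractions.** 0.17 + 1/18 gives 28.4%, 0.17 + 1/17 gives 29.7% and 0.17 + 4/34 gives 55.5%.

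**Step 4: direction of the uncertainty.** The rates in 1.5.5 are for SD lasting over 24 weeks. Section 9.2.1 sets no minimum duration, and Section 7.4 schedules assessment "beginning 12 weeks (+/- 7 days) relative to the first dose of study treatment". In any one population, SD counted without a minimum duration cannot be less frequent than SD over 24 weeks.

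**The case against.** Five points can be made on the other side.

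1. **The SD rates are borrowed.** They are for melanoma on nivolumab alone, in dose groups with response rates of 28% to 41%, and they are added here to a 17% Merkel cell rate. The 12% comes from the 1 mg/kg group, whereas Section 1.4.5 equates 240 mg with 3 mg/kg, where the figure is 1/17 and the result 29.7%. Section 1.5.5 gives SD for three of five dose groups. Pooling those three (6/69) gives 42.0%. Assuming no SD in the other two (6/106) gives 28.8%. This stands as a limit on precision, since the true size is unknown. Even the lowest of these figures is nearly three times the planned 10%.
2. **Type I error is a loose label.** If the null were 17% on CR+PR+SD, the error would still be 9.8%. That is correct. The quantity computed is the chance of passing when CR+PR is 17% and SD is also counted. But the plan derives no null for CR+PR+SD, and that mismatch is the problem.
3. **The natural reading is CR+PR.** Sections 1.4.3 and 9.1 and the synopsis all point that way, and 1.5.5 reports SD as additional to response. This supports the proposed correction. It does not remove the explicit sum in 9.2.1, which is the formal endpoint definition, and no rule of precedence says the synopsis overrides it.
4. **Confirmation and irRECIST need not be repeated in Section 9.** This is one combined document and the synopsis states both, so their absence from Section 9 matters little on its own.
5. **The denominator is a separate and smaller point.** The Analyses sentence in the synopsis goes on to a log-rank test and may be a mislabelled PFS sentence. The conflict remains without it: the synopsis itself uses treated patients in one place and all randomized in another.

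**Conclusion.** The concern holds. The definition in 9.2.1 contradicts the synopsis and does not match the design rates, and applying it literally to the Simon rule would undo the stated error control. With true CR+PR of 17%, the per-arm pass probability rises from 9.8% to between 30% and 57% at SD of 6% to 12% (28% to 55% with unrounded fractions). The probability of naming B the winner rises from 8.9% to between 22% and 28%.

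These figures assume that SD is counted in the rule, that CR+PR and SD rates are the same in both arms, and that the melanoma SD rates serve only as a range, because the document gives none for Merkel cell carcinoma. The contradiction depends on none of these assumptions. It must be corrected, because early stopping, the efficacy conclusion and the choice of winner all rest on this definition.

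**What to change.** - **9.2.1 and 9.3.2.1:** define ORR as confirmed CR or PR by irRECIST, assessed on non-irradiated target lesions.
- **9.1.1:** add a clause saying that a response in the two-stage rule and in the posterior comparison has this meaning.
- **Disease control:** report CR+PR+SD as a separate, named disease control rate.
- **Denominator:** choose one analysis set for ORR, use it throughout the synopsis and Section 9, and give the other as a sensitivity analysis.

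The cost is one sentence each in 9.2.1 and 9.3.2.1, one clause in 9.1.1, and the denominator phrase wherever it differs. No extra patients or data are needed, and the sample size and cut-offs stay as they are.

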6.5.4 Contouring of the Target Lesions

The primary endpoint of this clinical trial is ORR of a non-irradiated lesion to the combination of immunotherapy and radiation therapy outside the field. In order to avoid the direct cytotoxic effect on the target lesion by scatter radiation, GTV of the target lesion will need to be contoured if within 10cm of the radiation field and ensure mean dose < 2Gy to the volume.

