7.4.1 Definitions

Progression is defined as progressive tumor lesions per immune-related RECIST (irRECIST) definition, or appearance of one or more new Merkel cell carcinoma lesions, which can be local or distant in location from the irradiated lesions.

Local Control of Irradiated Lesion:

Progression of the irradiated tumor lesion is associated with aggressive tumor biologic features and resistance to radiation therapy.

Measurable Disease per irRECIST:

Measurable lesions must be accurately measured in at least one dimension (longest diameter in the plane of the measurement to be recorded) with a minimum size of:

- 10 mm by CT/MRI scan - (CT/MRI scan slice thickness no greater than 5 mm)
- 10 mm caliper measurement by clinical examination (lesions which cannot be accurately measured with calipers should be recorded as non-measurable)
- 20 mm by chest x-ray.

Malignant lymph nodes: to be considered pathologically enlarged and measurable per RECIST 1.1, a lymph node must be ≥ 15 mm in short axis when assessed by CT scan (CT scan slice thickness recommended to be no greater than 5 mm).

If the measurable disease is restricted to a solitary lesion (visceral or nodal), its neoplastic nature must be confirmed either by cytology/histology or by lesion progression certified on the next CT/MRI examination.

Nonmeasurable Disease per irRECIST:

Nonmeasurable lesions include all other lesions, including small lesions (longest diameter < 10 mm or pathological lymph nodes with ≥ 10 and < 15 mm short axis), as well as truly nonmeasurable lesions. Lesions considered truly nonmeasurable include: leptomeningeal disease, ascites, pleural or pericardial effusions, inflammatory breast disease, lymphangitic involvement of skin or lung, abdominal masses/abdominal organomegaly identified by physical exam that is not measurable by reproducible imaging techniques.

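### The plan defines the primary endpoint in two conflicting ways, as response of non-irradiated target lesions and as confirmed patient-level response by irRECIST, and never says how new or non-target progression enters the responder count.

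*Combined protocol and SAP*

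**What the plan says.** Two families of text describe the primary endpoint.

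**Lesion level.**
- Section 9.2.1, the only definition of the primary endpoint within Section 9, adds the rates of complete response, "partial response and stable disease of non-irradiated target lesions".
- Section 6.5.4 says "The primary endpoint of this clinical trial is ORR of a non-irradiated lesion".
- Section 1.4.3 justifies the choice of endpoint by the responses of target lesions.

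**Patient level.**
- The synopsis (Study Assessments) defines ORR as the percentage of patients with a complete or partial response, confirmed at a later assessment by irRECIST, "among all the patients who received at least one dose of nivolumab and ipilimumab with or without SBRT".
- Section 7.4.1 defines progression as progressive lesions by irRECIST "or appearance of one or more new Merkel cell carcinoma lesions".
- Section 7.4 has patients assessed for both target progression and new metastases, every 12 weeks in the first year.

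Section 9.3.2.1 gives the estimation method (exact binomial interval, at least one dose) and lists stable disease within ORR. It has no overall-response rule.

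The design rates are response rates without a scoring rule. Section 9.1 says "the estimated objective response rate with Nivolumab alone is estimated around 17"%, from trials of other PD-1/PD-L1 agents, and Section 9.1.1 says "We will use 40% response rate as a promising result to pursue further study".

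**The concern.** The two definitions can classify the same patient differently. Suppose a spared node is 40% smaller at weeks 12 and 24, and a new liver metastasis appears at week 12. On the wording of 9.2.1 alone, only the node matters and it has responded. Under 7.4.1 the patient has progressed, and under 9.2.2 that is a PFS event. The synopsis, with its patient-level irRECIST response, may exclude the patient, but the rule that would do so is not written out. An analyst working from Section 9 has no text that decides the case.

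The design makes the question more than formal. Section 3.1 asks for only two distinct lesions. In Arm B, Section 6 allows one to four metastases to be irradiated, with larger ones preferred, and the synopsis requires only that at least one target lesion be spared. An Arm B patient with two lesions may therefore be scored on one, while an Arm A patient with the same disease may be scored on both. Section 5.5.9 also allows treatment beyond first progression, so later scans showing a shrinking target are possible.

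At stake is the Simon rule in each arm. It needs only 7 responders of 24, and its error rate is calibrated to a 17% response rate, so a few points of extra scored response matter.

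**Working it through.** **Inputs.** From Section 9.1.1:
- null rate 17% and target rate 40%, "using a Simon Mini-Max two-stage design with 10% type I error rate and 10% type II error rate";
- a first stage of 16 per arm, after which the arm stops with 2 or fewer responders;
- otherwise 24 in total, and the arm fails with 6 or fewer.

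**Formula.** With true scored response rate p, the chance that an arm passes is

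P(pass) = sum over x = 3 to 16 of Bin(x; 16, p) × P(Y ≥ 7 − x), where Y is binomial (8, p).

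**The plan's own figures first.**
- At p = 0.17, P(pass) = 0.0978. At p = 0.40 it is 0.9013. Both meet the stated 10% error rates, and a grid search returns 2/16 and 6/24 as the minimax design.
- With the beta(1,1) priors and the 0.8 threshold, the exact chance of choosing Arm B is 85.5% at 40% versus 17% (stated 85%), and 8.85% at 17% in both arms (stated 8.89%, by simulation).

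The design is therefore correct for whatever response rate is fed into it.

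**Effect of the literal reading.** Let s be the share of target-lesion responders (CR or PR) who have new or non-target progression at the same time. Assume that every patient-level responder is also a target-lesion responder. If the patient-level CR+PR rate is 17%, the scored rate is 0.17/(1 − s). The documents give no value of s, so the range is an assumption.

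| s (assumed) | Scored rate | P(inactive arm passes) |
|---|---|---|
| 0 | 17.0% | 9.8% |
| 5% | 0.17/0.95 = 17.9% | 12.1% |
| 10% | 0.17/0.90 = 18.9% | 15.0% |
| 15% | 0.17/0.85 = 20.0% | 18.7% |
| 20% | 0.17/0.80 = 21.3% | 23.2% |

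At s = 15% in both arms (20.0% scored in each), the chance that Arm B is declared winner is 15.3%, against 8.85% at s = 0.

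**Under the synopsis.** If patient-level irRECIST response is what is scored, s has no effect and the first row applies.

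**What the table leaves out.** It uses CR+PR only, so that the target-lesion question stands apart from the stable-disease wording in the same sentence of 9.2.1. That wording has a larger effect. If an assumed 10, 20 or 30% of patients had stable disease on top of 17% CR+PR, an inactive arm would pass with probability 47.8%, 83.9% or 97.5%.

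**The case against.** The strongest reply is that 9.2.1 was never meant to work alone. It gives no size threshold and no confirmation rule, so calling the node in the example a partial response already borrows criteria from elsewhere in the protocol. Having borrowed those, one should also take the patient-level count and the treatment of new lesions. On this view the reference to non-irradiated target lesions only says which lesions are measured. Section 6 supports that, since it deliberately leaves irradiated lesions out of measurable disease, and 6.5.4 is about contouring and scatter dose.

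Much of this stands. A reader might infer that the plan does count a patient with new or growing disease as a responder, that the Simon rule is therefore easier to pass than stated, and that complete response rates are overstated. The documents do not support any of these as fact. No section says such a patient is a responder. Under the synopsis definition the inflation may be zero. Section 9.1 does not say how the trials behind the 17% scored new or non-target disease, so a mismatch with that benchmark cannot be shown either. The range for s is wholly assumed, and because the table sets stable disease aside, it is not the full error rate under 9.2.1 as worded.

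The reply does not remove the conflict. Three sections use lesion-level wording, and one of them is the governing statistical definition. The new-lesion clause in 7.4.1 defines progression, which 9.2.2 uses for PFS; nothing carries it into the responder count. Section 5.5.9, which offers example wording dating progression to the first event when treatment continues, is also silent on response. No section states how target, non-target and new lesions combine.

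**Conclusion.** The point holds as a conflict of definitions. Section 9.2.1, with 6.5.4 and 1.4.3, describes response of non-irradiated target lesions. The synopsis describes confirmed patient-level response by irRECIST. The two can disagree for a patient whose target shrinks while other disease progresses.

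The cost is conditional. If the literal reading of 9.2.1 were applied, and if 5 to 20% of target-lesion responders had such progression, the per-arm false-pass probability would be 12.1 to 23.2% instead of 9.8%. If the synopsis definition is applied, the plan's error rates stand. Excluding irradiated lesions from scoring is deliberate and is not at fault. This should be settled before the primary analysis, but it matters less than the inclusion of stable disease in the same definition, which is a separate defect.

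**What to change.** State one primary endpoint and use it throughout: confirmed best overall response of CR or PR per patient by irRECIST, with target response measured on non-irradiated lesions. Write out the irRECIST overall-response rule to be used, because the documents do not reproduce it. The rule should show how new Merkel cell lesions and progression of non-irradiated non-target disease change the patient's response at each assessment.

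Bring into line the synopsis (Study Assessments) and Sections 1.4.3, 6.5.4, 7.4.1, 9.2.1 and 9.3.2.1. Changing only 9.2.1 and 6.5.4 would leave 1.4.3 and 9.3.2.1 in conflict with the new text. Remove stable disease from ORR in 9.2.1 and 9.3.2.1 in the same amendment. Keep target-lesion-only response as a supporting endpoint for the abscopal question.

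The cost is wording. Target progression and new metastases are already assessed on the Section 7.4 schedule, so no new visits or scans are needed. The observed ORR may be slightly lower than under a target-lesion-only count.
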